### Research Plan/Approach:

#### **Subject selection and recruitment.**

These observational clinical studies will be conducted on individuals with AERD and CRSwNP who are referred to the BWH Allergy or Otolaryngology Clinics. For the surgically excised sinus tissue, patients undergoing sinus surgery will be screened to determine if they meet criteria: a diagnosis of CRSwNP, no history of cystic fibrosis or primary ciliary dyskinesia, and no unilateral nasal polyposis. Patients for this study will also be excluded if they are on any targeted respiratory biologic therapy, or on chronic oral steroids or other immunosuppressive agents. Those who meet criteria and want to participate will sign informed consent as approved by the Mass General Brigham IRB [the research proposed here is already covered under our existing IRBs, with #2019P001829 (Collection and Analysis of Healthy Sinus Mucosa and #2003P002088 (Analysis of Cells and Mediators from Aspirin-Tolerant and Aspirin-Intolerant Donors)].

Subjects will be between the ages of 18-65 years old, and we will aim to have equal numbers of male and female participants for each of the research approaches proposed below. A full physical exam, along with pertinent medical history, concomitant medications, prior history of response to medications, and prior surgical history will be collected for all participants.

For some portions of the proposal, tissue and cell samples have already been collected and are available for analysis in our tissue repository of human surgical samples (Aim 1a), and for others (Aim 1b and 2) all samples will be prospectively collected.

#### **SPECIFIC AIM 1: Characterize the plasma cell subsets, and the functional significance of their IL-5Ra, in nasal polyps from patients with CRSwNP and/or AERD.**

**Overview.** Nasal polyp tissue from patients with AERD contains a distinct population of plasma cells when compared to CRSwNP, marked by increased *IL5RA* expression. In this Aim we will test the **hypothesis that a unique subset of IL-5-responsive nasal polyp plasma cells drives the proliferation of sinus tissue plasma cells and the production of pathogenic antibodies in the respiratory tract of patients with CRSwNP and AERD.**

To identify transcriptional, cytofluorographic, and functional characteristics of plasma cells from nasal polyps in AERD and CRSwNP, we will employ two approaches, (1) RNA sequencing and (2) functional studies. We will then use qPCR and flow cytometry to verify the results on a set of markers selected based on pathobiologic interest, including IL-5Ra.

#### **Sub-Aim 1a. Use RNA sequencing to characterize the transcriptional profile of nasal polyp plasma cells in nasal polyps from patients with AERD and aspirin-tolerant CRSwNP.**

**Methods.** Sinus tissue from 6 subjects with AERD and 6 subjects with aspirin-tolerant CRSwNP has been obtained. Subjects were be matched for age, gender, and intranasal corticosteroid use. Freshly excised tissue was digested into a single cell suspension. Using a

BD FACSaria Fusion Cell Sorter, plasma cells were purified and collected in TCL buffer for storage. Going forward, 1000 cells from each patient phenotype will be used for low-input RNA sequencing, and the remainder set aside for qRT-PCR analysis. RNA will be sequenced with Smart-seq2 using the Broad Institute Technology Labs facilities. Unbiased differential gene expression will be characterized using the Kallisto program to map reads to the genome, taking into account uncertainty in read mapping. To identify gene sets that may relate to biologically relevant differences in cellular function we will utilize linear mixed models. To confirm expression results from our RNA sequencing, we will validate the gene quantification of the top 5 differentially expressed genes within the plasma cell populations with qRT-PCR, using commercially available primers.

**Anticipated Results.** We expect that the transcriptional signature of the plasma cells from patients with AERD will show increased cell survival and activation. We expect that these cells will show upregulation of transcripts involved in activation of the cell cycle (*CCND2*), antiapoptotic genes (*BCL2*, *CFLA/R*), and those encoding surface receptors and adhesion molecules (*IL5RA*, *ICAM1*, *CD9*), along with downregulation of negative regulators of the cell cycle (*KLF2*, *KLF6*). We predict that the plasma cells in nasal polyps from patients with AERD will have higher *IL5RA* expression overall, and will express more *IGHG4* and *IGHE* transcripts, suggesting that the overproduction of nasal IgE in inflamed tissues may be driven in part by IL-5 signaling.

**Sub-Aim1b. Determine the functional significance of IL-5R $\alpha$  expression and IL-5 signaling on the plasma cells in nasal polyp tissue.**

**Overview.** To exert effects, IL-5 induces phosphorylation and activation of several JAK and STAT proteins, and may be involved in regulation of transcripts involved in B-cell maturation, differentiation, and survival. While IL-5 supports murine plasma cell survival, IL-5-driven survival of human plasma cells has not been demonstrated. Our preliminary data has confirmed that IL-5R $\alpha^+$  plasma cells are enriched in nasal polyps, suggesting a disease-specific mechanism that may sustain antibody production. Moreover, our studies suggest that IL-5 can upregulate expression of transcripts involved in proliferation, survival, migration and class switch in these cells. In this Sub-Aim, we will test the **hypothesis that IL-5 stimulation of nasal polyp plasma cells induces signaling (A) and regulates transcriptional activity relevant to pathogenetic function (B)**.

**Methods.** **(A)** To determine the signaling capability of IL-5R $\alpha$  on nasal polyp plasma cells, we will measure the phosphorylation status of their JAK1/JAK2 and STAT1/STAT5, which are rapidly activated upon IL-5 binding to IL-5R $\alpha$  and can be surrogates of IL-5R $\alpha$  signaling *in vivo*. We will prospectively collect surgical samples and digest nasal polyp tissue from 5 AERD patients and 5 CRSwNP patients into a single cell suspension as above, and sort plasma cells as CD38 $^{HI}$ /CD27 $^{HI}$ /CD138 $^+$ /CD20 $^-$ . These will be evaluated using intracellular flow cytometry for phosphorylated JAK1, JAK2, STAT1, and STAT5. We will first measure the phosphorylation levels on freshly isolated cells, to determine differences in their baseline *in vivo* status. We will also measure their phosphorylation levels following a 6h and 24h stimulation with or without IL-5 (1, 10 and 100 ng/mL), as described previously, to confirm their IL-5R $\alpha$  signaling capacity. We will use BD Phosflow™ to optimize fixation and permeabilization for flow cytometric analysis of intracellular phosphoproteins. **(B)** To verify the transcriptional consequence of IL-5 signaling on plasma cells, we have already collected and sorted nasal polyp plasma cells from 5 patients with AERD and 5 CRSwNP and stimulated them for 6h with or without IL-5 (1, 10 and 100 ng/mL). The stimulated/unstimulated pairs of plasma cells have been collected in TCL buffer,

and banked for low-input RNA sequencing as above. Going forward, we will conduct differential expression analysis on IL-5-stimulated and unstimulated plasma cells using sample pairing, with a linear model framework. Our criterion for transcripts induced or repressed by IL-5 is that genes are more than twofold changed and obtain a false discovery rate of <1%.

**Anticipated Results.** **(A)** Plasma cell populations with higher IL-5R $\alpha$  expression should exhibit increased phosphorylation of JAK1, JAK2, STAT1, and STAT5 and should demonstrate further increases upon stimulation with IL-5. **(B)** We expect to confirm that IL-5 stimulation of nasal polyp plasma cells induces expression of *CCND2*, *JAK1*, *IKZF1*, *ZBTB44*, *OTG*, *RAP1B*, and *RAC2*, as well as signatures reflecting activation and anti-apoptotic signals (*BCL6*, *AID*, *BLIMP-1*).

**Statistical Analyses.** With a sample size of 6 AERD subjects and 6 CRSwNP subjects, we will be powered at >90%, at a 0.05 level of significance, to detect a difference in antibody-secreting cells that express IL-5R $\alpha$ + between subjects with AERD and CRSwNP. The data will be analyzed as described in Aim 2.

**Pitfalls and Alternative Approaches.** Although the proposed work is largely hypothesis based and furthers recent preliminary observations made by our group, low-input RNA sequencing allows for unbiased analyses. Thus, while we focus on the role of IL-5R $\alpha$ + plasma cells in CRSwNP and AERD pathogenesis, our approach also allows us to identify a range of differentially expressed genes and to broadly phenotype nasal polyp plasma cells.

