*CXCL1*, *IL10RA*, *IL1RL1* (ST2), and *IL6R*, as these transcripts are known to be impacted by IL-5 stimulation in the lower airway. We will also measure IL-5R $\alpha$  protein levels by Western-blot in these epithelial cells. To more broadly assess the effects of IL-5 signaling on human nasal polyp epithelial cells and to assess for yet-unidentified impacts of IL-5/IL-5R $\alpha$  signaling on these cells, we will collect IL-5 stimulated/unstimulated sinus tissue epithelial cell pairs for bulk RNA-sequencing with Smart-seq2.

**Anticipated results.** We suspect that the sinus tissue epithelial cells from diseased patients (CRSwNP and AERD) will express higher levels IL-5R $\alpha$  compared to healthy control tissue, and/or that their development of IL5RA expression will happen earlier in the maturation process compared to healthy control epithelial cells. We suspect that IL-5 stimulation of sinus tissue epithelial cells will identify downregulation of transcripts related to cellular adhesion and tight junction pathways and enrichment of a T2 immune signature.

**Statistical Analyses.** Differential expression analysis of RNA-seq data will be conducted using the DESeq2 package for R taking patient origin into account. Following normalization, DESeq2 will be run in a pairwise manner by comparing stimulated/unstimulated cell pairs, identifying significantly differentially expressed genes (DEGs). For pathway analyses, WebGestalt online tool will be used to identify the distribution of pre-ranked DEGs involved in specific signaling pathways in Gene Ontology Biological Processes database.

**Pitfalls and Alternative Approaches.** The molecular analysis of human upper airway epithelial cells is based on prior study of the human bronchial epithelial cells. However, if the pre-selected qPCR markers do not detect measurable differences between IL-5 stimulated and unstimulated cells, RNA-sequencing allows for unbiased analyses and may detect yet-undescribed changes mediated by IL-5. Further, if the molecular analyses do not identify IL-5-elicited changes in sinus tissue airway epithelium, we can plan functional phosphorylation studies on the sinus tissue airway epithelial cells as described in **Aim 1b**.

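### Does an RNA-seq input of 1000 cells per patient phenotype leave Sub-Aim 1a without subject-level libraries?

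*Combined protocol and SAP*

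**What the plan says.** The Methods of Sub-Aim 1a describe the material: "Sinus tissue from 6 subjects with AERD and 6 subjects with aspirin-tolerant CRSwNP has been obtained". On the design they add: "Subjects were be matched for age, gender, and intranasal corticosteroid use". Plasma cells were sorted and stored. The input for sequencing is then fixed: "Going forward, 1000 cells from each patient phenotype will be used for low-input RNA sequencing", "and the remainder set aside for qRT-PCR analysis". The five genes that differ most are to be validated by qRT-PCR.

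On analysis, Sub-Aim 1a says: "To identify gene sets that may relate to biologically relevant differences in cellular function we will utilize linear mixed models". The Statistical Analyses paragraph that closes Aim 1 adds: "The data will be analyzed as described in Aim 2". The matching paragraph in Aim 2 reads: "Differential expression analysis of RNA-seq data will be conducted using the DESeq2 package for R taking patient origin into account". It goes on to describe comparisons of stimulated with unstimulated cell pairs.

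Two later paragraphs bear on how samples are handled. The paragraph on blinding has every patient-derived sample stored and analysed under a random subject number, with disease state concealed until the mechanistic analyses are finished. The paragraph on confidentiality of genetic data gives isolated cell populations a numerical code whose key leads back to the individual subject.

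**The concern.** The input is stated for a unit, the phenotype, of which there are only two. Nothing nearby says how many libraries will be made or whether cells from different subjects stay separate.

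If cells were pooled by phenotype, there would be one library per group. Variation between subjects could not be estimated, and no valid test of AERD against CRSwNP would exist. Linear mixed models need replication within groups, and a bulk library that mixes patients has no single patient origin. This sequencing also selects the genes for qRT-PCR, and the cells it uses are no longer available for that validation. The sequencing is still to come, and pooled cells cannot be separated again.

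**Working it through.** **Inputs.** From Sub-Aim 1a, Methods: 6 + 6 = 12 subjects, 2 phenotypes, 1000 cells. Not given anywhere: the number of libraries and the sorted yield per subject. There is therefore no library count of the plan's own to reproduce. The only power figure for Aim 1 (above 90% with 6 against 6) concerns a different endpoint, the antibody-secreting cells that express the IL-5 receptor, and is not used here.

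**Step 1: what each reading implies.** Residual df = libraries - 2 groups.

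| Reading | Libraries | Cells per subject | Total cells | Residual df |
|---|---|---|---|---|
| A. One pool per phenotype | 2 | 1000/6 ≈ 167 if shared equally | 2 × 1000 = 2,000 | 2 - 2 = 0 |
| B. 1000 cells shared by six separate libraries | 12 | 1000/6 ≈ 167 (17% of 1000) | 2,000 | 12 - 2 = 10 |
| C. 1000 cells from each subject | 12 | 1000 | 12 × 1000 = 12,000 | 12 - 2 = 10 |

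If the matching forms six one-to-one pairs and is analysed that way, B and C have 6 - 1 = 5 df. These are simple two-group counts, not the exact df of DESeq2 or a mixed model. What matters is that A gives zero, while B and C do not.

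**Step 2: which readings the rest of the plan allows.**

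- *Matching of subjects* is a subject-level design. A pool of six could use it only as balance between the two groups.
- *Linear mixed models for gene sets* need several libraries per group. Reading A offers one; B and C offer six.
- *The Aim 2 method*, reached through the cross-reference, requires the patient behind each library to be known. That is impossible under A. The support is indirect, because the Aim 2 text is written for stimulated/unstimulated pairs and Sub-Aim 1a has none. With one library per subject, a separate term for each of 12 patients would use up all 12 observations. The natural adaptation is to put phenotype in the model and let subjects be the replicates.
- *Sub-Aim 1b* refers back to the same sequencing procedure, and there "we will conduct differential expression analysis on IL-5-stimulated and unstimulated plasma cells using sample pairing, with a linear model framework". Samples are kept separate in the workflow that borrows from Sub-Aim 1a.
- *Subject coding*: samples are to be analysed under a subject number, and isolated cell populations carry a code that traces to a subject. A pool of six patients has no such number.
- *Blinding*: pooling by disease group would require group membership to be used before sequencing, whereas disease state is to stay concealed until later. Coded group labels could get round this, so it counts as secondary evidence.

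None of these items states the number of libraries. Together they leave reading A with no support beyond the one phrase.

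**Step 3: whether the choice between B and C matters for validity.** Both keep 6 against 6 independent subjects. They differ in input per library (about 167 or 1000 cells) and in total use (2,000 or 12,000, a difference of 10,000). The documents do not say that 167 cells would be too few or that 12,000 would exhaust the stored material. They do expect cells to be left over for qRT-PCR.

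**The case for a change.** The best case for a change is that whoever prepares the libraries works from the Methods sentence, not from the confidentiality paragraphs. Taken literally, that sentence permits the one arrangement that defeats the comparison, and the error could not be undone in the analysis. Making replicate libraries from each pool would not rescue it. Suppose six replicates per pool were treated as six subjects. Simulation puts the nominal 5% type I error at about 7.5%, 15% and 34% when between-subject variance is 20%, 50% and 80% of the total. Correcting the wording would cost almost nothing.

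Part of this stands. The phrase is imprecise, the arithmetic for a pooled design is right, and the cross-reference to Aim 2 does not by itself define the unit for Sub-Aim 1a.

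The consequences, however, all need a step that the plan does not describe. Zero degrees of freedom requires physical pooling. The inflated error rates require, in addition, replicate libraries from each pool, and their variance shares are assumptions. The worry about using up stored cells requires yields that nobody has reported. Whether the matching is analysed as pairs is a separate question of how much detail to write down; an unpaired comparison of 6 with 6 remains available either way.

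**Conclusion.** This is a slip of wording and a missing detail, not a flaw in the design. Six subjects per group were sampled, and the matching, analysis, coding and blinding provisions fit subject-level libraries. Followed as a whole, the plan gives 12 libraries and 10 residual degrees of freedom in a simple two-group count (5 if analysed as six pairs). It does not give 2 libraries and none. The remaining ambiguity is the input per subject, between about 167 and 1000 cells, and neither end invalidates the comparison.

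The conclusion rests on two assumptions: that cells from different subjects are not combined, which the text implies without saying so, and that yields allow usable libraries from all 12 subjects, which cannot be checked from the documents. Writing subject in place of phenotype would be a reasonable editorial correction, but it would not alter the planned analysis.

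### Sub-Aim 1a's pattern of higher IL5RA with higher IGHE/IGHG4 in AERD can arise with no IL-5 effect on IgE; report it as an association and name the two transcripts in the paired experiment of Sub-Aim 1b(B)

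*Combined protocol and SAP*

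**What the plan says.** Sub-Aim 1a (Methods) is a between-disease comparison: "Sinus tissue from 6 subjects with AERD and 6 subjects with aspirin-tolerant CRSwNP has been obtained". Donors were "matched for age, gender, and intranasal corticosteroid use". Under Anticipated Results, AERD plasma cells "will have higher *IL5RA* expression overall, and will express more *IGHG4* and *IGHE* transcripts". The plan then interprets that predicted pattern as "suggesting that the overproduction of nasal IgE in inflamed tissues may be driven in part by IL-5 signaling".

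The Overview of Specific Aim 1 states that AERD polyp tissue "contains a distinct population of plasma cells when compared to CRSwNP, marked by increased *IL5RA* expression".

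IL-5 is varied only in Sub-Aim 1b. In part (B), plasma cells from 5 AERD and 5 CRSwNP donors were sorted and the investigators "stimulated them for 6h with or without IL-5 (1, 10 and 100 ng/mL"). The planned analysis is "differential expression analysis on IL-5-stimulated and unstimulated plasma cells using sample pairing, with a linear model framework", with a gene counted as responsive if it changes more than twofold at FDR below 1%. The Anticipated Results for (B) begin "We expect to confirm that IL-5 stimulation of nasal polyp plasma cells induces expression of" and then list CCND2, JAK1, IKZF1, ZBTB44, OTG, RAP1B and RAC2, with BCL6, AID and BLIMP-1 as activation and anti-apoptotic signatures. IGHE and IGHG4 are not listed.

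**The concern.** The 1a sentence moves from two group differences to a mechanism. Sub-Aim 1a describes no IL-5 exposure, no IL-5 measurement, no comparison of IL5RA-positive with IL5RA-negative cells, and no donor-level association between IL5RA and IGHE. Any two transcripts that both differ by disease would give the predicted result, whether or not IL-5 acts on IgE. The Aim 1 Overview supplies one such route: if the distinct AERD plasma-cell population carries more IGHE for some other reason, both transcripts rise together.

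At stake is how the result is read. The confirmed pattern could be taken as support for an IL-5 effect that it cannot separate from coincident disease effects. Meanwhile the within-donor data that bear more directly on the question would pass through a screen with little power for two genes of prior interest.

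**Working it through.** **1. The plan's own figure.** Statistical Analyses under Aim 1 states more than 90% power with 6 v 6 at the 0.05 level. No difference or SD is given, so this can be neither reproduced nor refuted. With 6 per group, 90% power needs a standardized difference of 2.08 (two-sided t-test) or 1.82 (one-sided t-test). The endpoint there is the frequency of IL-5Rα-positive antibody-secreting cells, not IGHE or IGHG4, so 2.08 SD serves below only as a scale.

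**2. Can the 1a pattern arise with no IL-5 effect?** Assume IL5RA and IGHE each differ by disease by d SD, with no effect of IL-5 on IGHE. For one transcript at 6 v 6, the noncentrality is d × √(6/2), with 10 df and a critical t of 2.23. If the two are uncorrelated within group, the chance that both are significantly higher in AERD is the square of the single-test power. A simulation of 40,000 runs gives the correlated case and the chance that both means are simply higher.

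| Assumed d (SD) | One test | Both significant, r = 0 | Both significant, r = 0.5 (simulated) | Both means higher |
|---|---|---|---|---|
| 1.0 | 0.347 | 0.347² = 12% | 19% | 92–93% |
| 1.5 | 0.650 | 0.650² = 42% | 49% | 99% |
| 2.0 | 0.876 | 0.876² = 77% | 79% | >99.9% |
| 2.5 | 0.973 | 0.973² = 95% | 95% | >99.9% |

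At d = 2.08 the result is 0.90 × 0.90 = 81%. With no disease difference at all, both are significantly higher in under 0.5% of runs. The alternative explanation is therefore confounding or cell composition, not chance.

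**3. What can 1b(B) detect for these two genes?** There are 5 + 5 = 10 donors. Assume a true twofold change (1 on the log2 scale) and a paired log2 SD s. The documents give no SD, so a range is shown. For a single paired contrast the noncentrality is (1/s) × √10, with 9 df. A per-gene level of 0.001 stands in for FDR below 1%; 0.025 is the first Holm step over two genes.

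| s (log2) | Noncentrality | Power at 0.001 | Power at 0.025 |
|---|---|---|---|
| 0.5 | 6.32 | 87% | >99% |
| 1.0 | 3.16 | 16% | 68% |
| 1.5 | 2.11 | 4% | 34% |

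These powers are before the fold-change filter. When the true change is exactly twofold, about half of the estimates fall below twofold, so the full screen cannot exceed about 50% even at s = 0.5. Fitting disease group leaves 8 df, and at s = 1.0 the powers become about 14% and 66%.

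**4. Would a within-group correlation in 1a help?** With 6 donors there are 4 df and a critical t of 2.776, so significance needs |r| = 2.776/√(2.776² + 4) = 0.81. Such a correlation would show little.

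**The case against.** The sentence sits under Anticipated Results and is hedged three times; no test or decision depends on it. A reader might infer that the plan draws a causal conclusion about IL-5 and IgE. It does not: it states a hypothesis, and the next section sets out IL-5 experiments.

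A reader might also infer that the within-donor question has no pre-specified analysis. That is not so. Sub-Aim 1b(B) fixes a paired model and a criterion that apply to every transcript, including IGHE and IGHG4. It lists AID, the closest named class-switch marker, and the 1b Overview cites preliminary evidence that IL-5 upregulates class-switch transcripts. What is missing is a targeted designation of two genes, not data or a model.

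The percentages in step 2 follow from assumed disease shifts, so they are not an error rate of the plan; at 1 SD the figure is only 12% to 19%.

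Finally, a 6-hour stimulation does not test the plan's main proposed mechanism, which is survival and proliferation of plasma cells. Sub-Aim 1b(B) therefore cannot be the sole arbiter of whether IL-5 contributes to nasal IgE.

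All of this stands, and it lowers the severity. It does not make the 1a pattern discriminating: hedging leaves the data unchanged, and nowhere is the IgE reading made conditional on 1b(B).

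**Conclusion.** The point holds as a minor one. The between-disease pattern is compatible with an IL-5 effect on IgE but does not distinguish it from disease differences without one, so it supports an association only. That rests on the design and on the plan's own description of a distinct AERD population; the simulated frequencies only illustrate it.

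The 1b(B) screen covers IGHE and IGHG4 with low power under plausible but assumed variability: about 16% against 68% at a paired log2 SD of 1.0. The gap in significance-test power is small at 0.5 (87% against more than 99%), though the twofold filter still costs about half there. At 1.5, power is poor either way (4% against 34%). These figures assume a true twofold change, 10 usable pairs, a single paired contrast, and 0.001 as a proxy for the FDR rule.

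**What to change.** - **Sub-Aim 1a.** Reword the sentence so that higher IL5RA together with higher IGHE/IGHG4 is reported as an association with AERD. Do not offer a within-group IL5RA–IGHE correlation as evidence.
- **Sub-Aim 1b(B).** Before the sequencing data are read, name IGHE and IGHG4 as donor-paired tests over all 10 donors, with disease group in the model. State one contrast across the three IL-5 concentrations in advance, for example a single dose-trend test with its scoring given. Apply Holm over the two genes and report estimates with confidence intervals. Keep the twofold and FDR rule for all other genes.
- **Interpretation.** Base any statement that IL-5 acts on IgE transcripts on that result and limit it to transcription at 6 hours. State that it does not test survival or expansion of IgE-producing cells, and that a null result is no evidence of an effect at 6 hours rather than evidence of no effect.

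The cost is a change of wording and two extra tests on samples already banked. The downside is a weaker claim from 1a.

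### The baseline JAK/STAT read in Sub-Aim 1b is offered as in vivo status, but as the steps are written it measures post-isolation status, so neither a null nor a positive baseline difference shows the status at surgery

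*Combined protocol and SAP*

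**What the plan says.** All of this is in Sub-Aim 1b, Methods (A), on samples still to be collected. The laboratory will "digest nasal polyp tissue from 5 AERD patients and 5 CRSwNP patients into a single cell suspension as above, and sort plasma cells as" a set of surface markers (high CD38 and CD27, CD138 positive, CD20 negative). The next sentence takes those sorted cells forward: "These will be evaluated using intracellular flow cytometry for phosphorylated JAK1, JAK2, STAT1, and STAT5".

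Two reads follow. The first is the baseline: "We will first measure the phosphorylation levels on freshly isolated cells, to determine differences in their baseline" status in vivo. The second tests capacity to signal: "We will also measure their phosphorylation levels following a 6h and 24h stimulation with or without IL-5 (1, 10 and 100 ng/mL").

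On kinetics, the plan says of these proteins only that they are ones "which are rapidly activated upon IL-5 binding to IL-5R"α. It says nothing about how fast the signal fades. On fixation it says only: "We will use BD Phosflow™ to optimize fixation and permeabilization for flow cytometric analysis of intracellular phosphoproteins". No time point is given relative to excision, digestion or sorting. The Pitfalls and Alternative Approaches paragraph of Aim 1 does not discuss signal change during processing.

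**The concern.** The baseline read has a different purpose from the stimulation read. Adding IL-5 in a dish shows that the receptor can signal; the baseline read is meant to show whether it was signalling in the patient. The Anticipated Results for (A) expect raised phosphorylation in populations with more IL-5Rα, with further increases once IL-5 is added, so a result is plainly expected from the unstimulated cells.

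The cells that are read have been through enzymatic or mechanical dissociation and a live sort, outside the tissue. Phosphorylation can change over those steps. If it does, the number reported as in vivo describes the cells at the end of isolation. An absence of difference could mean none at surgery or one lost on the bench. A difference could have been present at surgery or produced by handling, for instance if processing times happened to differ between the two groups of five. The planned data cannot tell these apart.

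**Working it through.** **1. Order of steps, side by side (Sub-Aim 1b, Methods (A)).**
- Digest to single cells, then sort on surface markers, then read the sorted cells by intracellular flow. This order is explicit.
- The sorted cells are also cultured for 6 h and 24 h, so the sort must be of live cells for those arms. Only one sort is described, and the baseline read is on freshly isolated cells from it. A live sort for the baseline is therefore the natural reading, though an inference.
- Fixation has no stated position. Nothing in the text fixes an aliquot earlier or records elapsed time.
- Stated target: status in vivo. Quantity measured: status after digestion and sorting. These differ unless processing leaves phosphorylation unchanged, which the plan neither shows nor plans to check.

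**2. Can the change be sized? Loss of signal.** No processing time T or half-life h is given, so both are assumed. With exponential decay, share left = 0.5^(T/h):

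| Assumed half-life | T = 1 h | T = 2 h | T = 4 h |
|---|---|---|---|
| 30 min | 25% | 6% | 0.4% |
| 1 h | 50% | 25% | 6% |
| 2 h | 71% | 50% | 25% |

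If the signal is sustained within the cell, the loss is small. If handling induces phosphorylation, the change goes the other way. The range is too wide to support any single figure.

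**3. What would that do to a 5 v 5 comparison?** The plan gives no power figure for phosphorylation. The only power statement (Aim 1, Statistical Analyses) is above 90% at 0.05 for IL-5Rα+ antibody-secreting cells, 6 v 6. It cannot be reproduced, because no effect size, SD or test is given. Solving backwards with a two-sided t test, 90% power at 6 v 6 needs a standardised difference d = 2.08. Borrowing that d purely for illustration, 5 v 5 has 82% power if nothing is lost.

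Let f be the share of signal left, the same for every patient, and b the share of the variance that is real between-patient signal and so shrinks with it. Then d after processing = 2.08 × f / √(1 − b + b f²). For f = 0.5 and b = 0.5: 1.04 / √(0.5 + 0.125) = 1.32. Power at 5 v 5, two-sided 0.05:

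| Share left | b = 0 | b = 0.5 | b = 0.8 | b = 1 |
|---|---|---|---|---|
| 50% | 31% | 45% | 63% | 82% |
| 25% | 11% | 17% | 31% | 82% |

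So even with half the signal gone, power could be anywhere from 31% to 82%, depending on a variance split the documents do not give. The calculation shows that loss can matter, not that it does or by how much. It also leaves out processing times that vary between cases, which could add noise or bias in either direction.

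**The case against.** The strongest reply is that the mechanism is not in the documents. The plan calls the signals rapidly activated, which says nothing about deactivation. The one remark that IL-5 is constantly present in CRSwNP sinuses is made for the epithelial cultures of Aim 2. Fixation timing is silence, not contradiction, and may be thought bench detail. The core of Methods (A) is signalling capability, which is tested with a concurrent unstimulated control. The baseline sentence does not name AERD v CRSwNP as its contrast, and the Anticipated Results are framed by IL-5Rα expression.

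Most of this stands, and it limits the point. A reader might infer that a real AERD v CRSwNP difference will decay and be reported as absent, or that power falls from 82% to 31%. The documents support neither. Processing may raise as well as lower phosphorylation. The 31% needs half the signal lost, none of the variance to be patient-level signal, and an effect size borrowed from another endpoint. The group contrast is a plausible use of the 5 v 5 sampling, not a stated estimand.

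What the reply does not remove is the mismatch. The order of steps is explicit, the read is on the sorted cells, and the plan calls the result in vivo status. Following the text as written gives a post-isolation value with no record from which the effect of handling could be judged.

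**Conclusion.** The concern holds as a mismatch between a stated objective and its measurement. The baseline read is post-isolation status. Neither a null nor a positive baseline difference can be taken as the status at surgery. The amount and direction of any distortion cannot be sized from the documents; the tables in the working are illustrations under assumed half-lives, processing times and variance shares.

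The conclusion rests on two readings of the text: that the single sort described is live for the baseline cells too, and that no earlier fixation is intended because none is written. If the laboratory already fixes before sorting, the plan should say so; the digestion step would still come first unless tissue is fixed.

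The scope is narrow. The 6 h and 24 h stimulated v unstimulated comparisons each have their own concurrent control and can still show signalling capacity. This is a worthwhile, low-cost improvement, not a fault in the sub-aim as a whole.

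**What to change.** For the baseline read only:
- Fix an aliquot before the sort, right after dissociation, or fix tissue earlier if the antibodies allow. Identify plasma cells by gating on the same surface markers instead of sorting first. Sort the remaining live cells for the stimulation arms as planned.
- Record the time from excision to fixation for every sample and report it by group as a descriptive sensitivity check. With 5 v 5 it should not go into a model as a covariate.
- Name the read for what it is. Digestion still precedes fixation of a post-dissociation aliquot, so call that read post-dissociation. If no aliquot is fixed, call it post-isolation. In both cases drop the in vivo claim.

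Cost: these samples are still to be collected, so this changes the order of steps and adds one recorded time. Some cells are diverted from the stimulation arms; how much that matters is unknown, because no plasma-cell yield is given. The surface markers must be checked on fixed cells, which can be done within the step the plan already has to "optimize fixation and permeabilization for flow cytometric analysis of intracellular phosphoproteins". The minimum version, renaming the read and dropping the in vivo claim, costs only a change of wording.
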